### **Secondary analysis**

Secondary analyses will be conducted using the ITT population. No adjustment for missing data will be performed when analysing these outcomes as no missing data is expected for them.

Secondary outcomes will be analysed in the same way as primary outcomes using multiple regression models with adjustment for stratification factors. The type of regression model will depend on the data distribution. All model assumptions will be assessed.

Number of readmissions and number of nights in psychiatric hospitalization are count outcomes and will be analysed using Poisson or negative-binomial regression models depending on data dispersion. Results will be presented as incident-density ratios, which are interpreted in the same way as relative risks.

The number of nights to first readmission from INDEX to 365 days, and time under compulsion, are time to event outcomes and analyses will be performed using proportional hazards regression, with results presented as hazard ratios with 95% confidence intervals. Kaplan Meier plots will also be presented and the median time to readmission calculated with 95% confidence intervals.

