### *Secondary outcomes*

Secondary outcomes related to readmission follow the same readmission definition and constraints stated for the primary outcome. Secondary outcomes considered in this study are mainly obtained from medical records. They represent patterns of readmission and are listed next.

**Number of nights in psychiatric hospitalization from INDEX to 365 days.** This will include voluntary and involuntary hospitalizations. Nights on recall will not be included.

**Number of nights to first readmission from INDEX to 365 days.** Time to first readmission for patients (in both arms) that remained in hospital for the duration of the trial will be counted as zero. Nights on recall do not count as a readmission.

**Number of readmissions from INDEX to 365 days.** This will include voluntary and involuntary hospitalisations but not nights on recalls.

**Time under legal compulsion.** This will be measured by time being subject to the Mental Health Act (i.e. under sections 2, 3, 17, 37 or on a CTO).

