#### **Target population**

##### *Inclusion criteria*

Patients were eligible if they were:

- Aged 18-65 years (in line with local administrative procedures for adult mental health services);
- Diagnosed with psychosis;
- Currently admitted under section 3 or section 37 (without restrictions) of the MHA;
- Not currently subject to any other legal restrictions;
- Judged by their clinicians (RC and AMHP) to need ongoing community treatment, but, having considered the relevant legal standards and clinical indicators, clinicians are genuinely uncertain as to which treatment mechanism would be appropriate;
- Able to consent to take part in research and give written and informed consent;
- Not having participated in the study (i.e. people with multiple admissions throughout the recruitment period should only participate in the study once).

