### **Description of treatments received**

For CTOs, the number of recalls and their lengths will be summarized. For both treatments, the time to initial discharge after randomisation and subsequent occurrences will be summarized according to:

- Number of hospitalisations;

- Average length of hospital stays;
- Changes to legal status;
- Total number of tribunals (MHRT);
- Total number of Managers Hearings;
- Number of recalls and revocations;
- Discharges;
- Average duration on CTO and on Section 17 Leave;
- Number of people who never leave hospital during the trial period;
- Number of patients whose voluntary hospitalisation is made involuntary during admission;
- Average number of service contacts received;
- Time under legal compulsion (including recalls);
- Number of
  - Face-to-face contacts with service;
  - Phone contacts with service.

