## ***9. Analysis of secondary outcomes***

### **Descriptive statistics for outcome measures**

For all secondary outcomes, we will report the number and percentage of observed values, mean and standard deviation, median and inter-quartile range, and range, by arm and full sample.

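### Time under legal compulsion is defined as an amount of time but analysed by proportional hazards regression with no event, origin or censoring rule, so the hazard ratio does not estimate the outcome

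*SAP*

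**What the plan says.** Section 2 (Secondary outcomes) says that time under legal compulsion will be "measured by time being subject to the Mental Health Act" and lists the statuses that count: sections 2, 3, 17 and 37, or a CTO. Unlike the other three secondary outcomes, its entry gives no window from INDEX to 365 days.

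Section 6 (Description of treatments received) lists the same variable among the quantities to be summarised in both arms, with recalls included. Section 9 (Descriptive statistics for outcome measures) gives every secondary outcome "mean and standard deviation, median and inter-quartile range, and range, by arm and full sample".

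Section 9 (Secondary analysis) sets the model: "The number of nights to first readmission from INDEX to 365 days, and time under compulsion, are time to event outcomes". Both are to be analysed by proportional hazards regression and reported as hazard ratios. The survival summaries that follow concern readmission only: "Kaplan Meier plots will also be presented and the median time to readmission calculated with 95% confidence intervals". The preceding paragraph treats nights in hospital as a count, with a Poisson or negative binomial model.

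**The concern.** A proportional hazards model needs an event, a starting point and a rule for patients in whom the event is not seen. Readmission supplies an event. Time under compulsion, as section 2 defines it, is a quantity pooled over several legal statuses that a patient may enter, leave and re-enter. The SAP does not say what event would turn it into a survival time. Its hazard ratio would not tell a reader how much more or less time patients in one arm spent under compulsion.

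This is the only secondary outcome that measures legal compulsion itself, and one arm is defined by a compulsory order in the community. Section 5 makes no adjustment to p values, so the hazard ratio and its p value would be reported at face value. The undefined event also leaves the choice between different analyses until the data are in hand.

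**Working it through.** The SAP states no figure for this outcome, so there is none to reproduce. The check sets the definition against the model and then tries each way of making the model work.

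**Definition against model**

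| Place in the SAP | How the variable is treated |
|---|---|
| Section 2, Secondary outcomes | Time subject to the Act, five statuses pooled, no event |
| Section 6, Description of treatments received | An amount, recalls included |
| Section 9, Descriptive statistics | Mean, SD, median, IQR and range |
| Section 9, Secondary analysis | Time to event, hazard ratio |
| Section 9, Secondary analysis, nights in hospital | A similar accumulated duration, modelled as a count |

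**Possible readings of the model**

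Take a patient with two spells totalling 165 days, the first lasting L days and the second still running at day 365.

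1. *Event is the first end of compulsion.* Entry requires "Currently admitted under section 3 or section 37 (without restrictions) of the MHA", so every patient starts under compulsion and this event is available. The patient is recorded as an event at L days, and the remaining 165 − L days are lost. Section 5 (Method for handling time-varying interventions) shows that legal status can change during follow-up.
2. *Total days, censored if still compelled at day 365.* The patient is recorded as more than 165 days, although 165 is the exact total.
3. *Total days, all complete.* The patient is recorded as 165. The hazard ratio then compares the two distributions of totals, but it is not a difference or ratio in days.

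**Illustration of reading 1 (all durations assumed, none from the SAP)**

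Patients alternate between on and off compulsion over 365 days, with exponential durations and 6,000 patients per arm. A hazard ratio below 1 means that compulsion ends more slowly in the first arm.

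| | Scenario A | Scenario B |
|---|---|---|
| First arm, mean days: first spell / gap / later spell | 150 / 600 / 60 | 180 / 300 / 60 |
| Second arm, mean days: first spell / gap / later spell | 100 / 150 / 90 | 90 / 300 / 60 |
| Mean total days, first v second arm | 152.6 v 177.7 | 183.6 v 125.6 |
| Ratio of means | 152.6/177.7 = 0.86 | 183.6/125.6 = 1.46 |
| HR, first end of compulsion | 0.67 | 0.50 |
| HR, total days, all complete | 1.07 | 0.54 |
| HR, total days, censored only if the total is 365 | 1.07 | 0.53 |

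In scenario A the first arm has 177.7 − 152.6 = 25.1 fewer days of compulsion, yet the first-end hazard ratio of 0.67 reads as longer compulsion. In scenario B all the hazard ratios agree in direction with the totals.

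**Illustration of reading 2 (equal totals in both arms, assumed censoring)**

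If both arms have the same distribution of totals and being censored is unrelated to the total, the event hazard in each arm is the common hazard multiplied by its uncensored fraction. Hence HR = (1 − c1)/(1 − c2), where c1 and c2 are the fractions censored.

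| Censored, c1 v c2 | Formula | Simulated HR (mean total about 137 days, 4,000 per arm) |
|---|---|---|
| 40% v 10% | 0.60/0.90 = 0.67 | 0.63 to 0.68 |
| 30% v 10% | 0.70/0.90 = 0.78 | 0.75 to 0.80 |
| 20% v 10% | 0.80/0.90 = 0.89 | 0.87 to 0.92 |
| none | 1.00 | 0.98 to 1.04 |

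Any departure from 1 here comes from the censoring imbalance alone. The SAP contains neither this censoring rule nor these percentages.

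**The case against.** The best defence is that a coherent survival outcome exists. Every patient is under compulsion at entry, so time from randomisation to the end of compulsion, censored at the end of follow-up, can be analysed by proportional hazards. The definition does not use the words total or days, and total days under compulsion is absent from the list of derived variables in section 5. This stands to the extent that the accumulated reading is an inference from the pooled statuses and from the summaries in sections 6 and 9. It does not rescue the plan: time to first end of compulsion is a different quantity from the one defined, and the SAP does not name it. A reader might infer that compulsion could never be a time-to-event outcome, but the documents do not support that.

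A reader might also infer that time per patient would never be reported. That is not so: section 9 plans means and medians by arm for all secondary outcomes. The gap is an adjusted between-arm contrast on the time scale, with its confidence interval.

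The illustrations rest on assumed inputs, and under reading 2 the assumed censoring fractions largely set the answer. This stands, so they show what could happen and do not predict a bias.

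Replacement models have limits too. Totals are bounded at 365 days and may pile up there, and deaths shorten observation. That also stands, and the fix should deal with it.

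The general statement that the model will depend on the data distribution does not help, because a later paragraph of the same section fixes the model for this outcome.

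**Conclusion.** The point holds: the plan is wrong as written for this outcome. The definition and summaries describe an amount of time, the model requires an event that is never named, and the hazard ratio does not estimate a difference or ratio in time under compulsion under any of the readings considered. The first-end reading ignores returns to compulsion. Censoring totals at day 365 turns exact values into lower bounds, possibly to a different degree in each arm.

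The conclusion rests on taking time subject to the Act as the total across spells, and on a 365-day window carried over from the other secondary outcomes. No size of bias can be taken from the SAP. A reader who treated the 0.67 in either illustration as an expected error would be going beyond the documents.

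Severity is moderate. One of four secondary outcomes is affected, it is already excluded from the subgroup analyses in section 5, and the primary analysis is untouched.

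**What to change.** 1. In section 2, define time under legal compulsion as total days from INDEX to 365 days spent under any of the listed statuses, with all spells added and recalls included as in section 6. State how days after death or withdrawal are handled, and add the variable to the derived variables in section 5.
2. In section 9, remove time under compulsion from the proportional hazards sentence. Analyse total days with adjustment for the three stratification factors, as a difference in mean days with a robust or bootstrap 95% confidence interval. The negative binomial model already planned for nights in hospital, giving a ratio of mean days, is an alternative; choose one in advance.
3. If time to first end of compulsion is also wanted, list it as a separate outcome with its own event, origin and censoring rule, and keep proportional hazards regression for that.

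The cost is a change of SAP wording. No new data are needed, since section 6 already plans to summarise time under compulsion, changes of legal status and time on each order.

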## ***10. Analysis of tertiary outcomes***

### **Descriptive statistics for outcome measures**

For all tertiary outcomes, we will report the number and percentage of observed values, mean and standard deviation, median and inter-quartile range, and range, by arm and full sample.

### **Tertiary analysis**

Tertiary analyses will be conducted using the ITT population once again. Where patient self-reported outcomes with missing data are analysed, these data will be imputed using multiple imputations (see Section 0).

For categorical outcomes such as self-reported adherence to treatment, substance misuse (CAGE), experience of specific types of leverage, and types of pressure chi-squared tests will be performed and no adjustments for stratification factors will be possible.

For continuous or pseudo-continuous outcomes (satisfaction with service (CSQ-8 and STAR-P), social and clinical outcomes (BPRS-24, GAF, EQ-5D, ITAQ, DAI-10, and API), service usage (CSRI), AES subscales, Index of fairness, and Index of effectiveness) linear regression models will be used.

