### *Tertiary outcomes*

Tertiary outcomes considered in this study are mainly self-reported patient outcomes. These are:

**Adherence to treatment.** This will be obtained from two self-reported variables recording how often, over the past month, the patient

- took his/her prescribed medication
- attended his/her planned appointment.

**Satisfaction with service.** This will be measured through the Client Satisfaction Questionnaire (CSQ-8) total score and Scale to Assess Therapeutic Relationships – Participant Version (STAR-P).

**Social and clinical outcomes.** These will be measured by the following instruments

- Brief Psychiatric Rating Scale (BPRS-24)
- Global Assessment of Functioning (GAF)
- Substance misuse history (CAGE)
- Health Related Quality of Life (EQ-5D)
- Insight and Treatment Attitudes Questionnaire (ITAQ)
- Drug Attitude Inventory (DAI-10)
- Psychiatry Autonomy Preference Index (API).

**Service usage.** This will be measured by the Client Service Receipt Inventory (CSRI).

**Patient rated experiences of pressure.** This will be measured by

- Mac Arthur Admission Experience Survey (AES)
- Index of fairness
- Index of effectiveness
- Experience of specific types of leverage questions.
- Types of pressure.

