### **Methods for handling missing data**

Given that the analysis is planned as an intention-to-treat analysis, data from all randomised patients will be included. Tertiary self-reported outcomes are likely to have missing values. For analysis involving these variables, missing data will be handled by multiple imputations using the *ice* stata command to generate a suitable number of imputed data sets and then using the *mim* stata command to automatically analyse each dataset and pool the results. The number of imputations will be chosen as follows:

- 1) The proportion of observed data will be calculated;
- 2) Assuming a tolerance for preventable power falloff <1%, a number of imputations  $m_I$  will be selected using Table 5 of Graham and colleagues' paper;
- 3) The proportion of information available will then be estimated using  $m_I$ ;
- 4) Table 5 will be used once again to obtain the final number of imputations  $m$  needed for the analysis.

The imputation model will potentially include all predictors of missing values (identified by fitting a logistic regression to each baseline variable on an indicator of missingness, for each variable with missing values), the primary, secondary and tertiary outcomes, and the stratification factors.

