### **Method for handling randomisation, stratification or minimisation factors**

Stratification variables (gender (male/female), schizophrenic status (yes/no), and duration of illness (< 2yrs, ≥ 2yrs)) will be adjusted for in the main analyses.

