### **Derived and computed variables**

Total scores for the following instruments will be automatically calculated previous to handing the data to the statistician:

- Substance Misuse History (CAGE) –Two scores will be calculated from 2x4 questions: 1) Positive for alcohol (y/n), and 2) Positive for drugs (y/n);
- Leverage - no total score but frequencies of those experiencing each type of leverage;
- MacArthur Admission Experience Survey (AES) –only total scores will be calculated for each of this instrument's subscales: 1) Perceived Coercion Scale; 2) Negative Pressures Scale, and 3) Procedural Justice Scale;

- Index of fairness;
- Index of effectiveness;
- Insight and Treatment Attitudes Questionnaire (ITAQ);
- Scale to Assess Therapeutic Relationship in Community Mental Health Care – Participants version (STAR –P) total score –and three subscale scores: 1) Positive Collaborations, 2) Positive Clinician Input, and 3) Non Supportive Clinician Input;
- Autonomy Preference Index (API) – only total scores will be calculated for the two subscales 1) Decision-making scale, and 2) Information Seeking Scale;
- Client Satisfaction Questionnaire (CSQ-8);
- Health Related Quality of Life Questionnaire (EQ-5D);
- Drug Attitude Inventory (DAI);
- Brief Psychiatric Rating Scale (BPRS);
- Global Assessment of Functioning (GAF).

Contact with service will be obtained by summing up questions 1-6 and 10 from the Client Service Receipt Inventory section of the CRF. The total number of contacts with carers of any profession will be calculated as well as the total number of phone and face-to-face contacts.

The following variables will be manually calculated previous to locking the dataset by comparing admission and discharge dates from (a) Index to 180 days; (b) 181 days to 365 days; (c) Index to 365 days:

- Number of nights to readmission;
- Total number of days in hospital;
- Total number of involuntary readmissions. A readmission will be considered involuntary if there is at least one change of status to “involuntary” between the admission and discharge dates;
- Total number of voluntary readmissions;
- Total number of CTO recalls.

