## ***11. Safety analyses***

Binary safety variables such as self-harm, death, harm to others or being a victim of crime will be analysed in the same way as the primary outcome using log-binomial regression.

Counts of safety variables (such as number of self-harm episodes, number of times a victim of crime, etc.) will be analysed as per secondary count outcomes using Poisson or negative binomial regression models. Cause of death will be tabulated descriptively by treatment group.

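### Categorical tertiary outcomes get only an unadjusted chi-squared test as their main analysis, although the SAP already uses adjusted models for binary outcomes; adherence loses its ordering and pooling after imputation is undefined

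*SAP*

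**What the plan says.** Section 10 (Tertiary analysis) sets one method for types of pressure, leverage, CAGE and adherence. It states that "chi-squared tests will be performed and no adjustments for stratification factors will be possible", and gives no reason for the second half of that statement. The same section sends self-reported outcomes with missing values to multiple imputation. Section 5 (Methods for handling missing data) says that this will rely on a "stata command to automatically analyse each dataset and pool the results".

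The scales of these outcomes are partly stated:

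- Section 5 (Derived and computed variables) reduces CAGE to two yes/no scores, one for alcohol and one for drugs.
- For leverage it specifies "no total score but frequencies of those experiencing each type of leverage".
- Section 2 (Tertiary outcomes) bases adherence, one item on medication and one on appointments, on "two self-reported variables recording how often, over the past month, the patient" did each. The response categories are not listed.
- The format of the types-of-pressure items is not given.

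Elsewhere, section 8 analyses the binary primary outcome by log-binomial regression adjusted for gender, schizophrenia status and duration of illness, with robust Poisson or logistic regression as fallback. Section 11 says that binary safety variables "will be analysed in the same way as the primary outcome using log-binomial regression". Section 1.3 makes adjusted regression the primary comparison because it is more precise, and leaves unadjusted tests to sensitivity analyses.

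**The concern.** A reader who follows section 10 will run an unadjusted test on yes/no items that the SAP's own adjusted model for binary outcomes could handle. That reverses the order of priority set in section 1.3, and the only justification offered is that adjustment cannot be done.

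Three things are at stake. First, a chi-squared test gives a p-value but no effect size or interval, so the report would have no planned estimate of how far CTOs change adherence, substance misuse or leverage. Adherence matters most here, because the secondary objective in section 2 names it as the route to fewer relapses and readmissions. Second, a general chi-squared test treats the adherence responses as unordered and spends degrees of freedom on patterns of no interest. Third, section 6 (Comparison of losses to follow-up) expects substantial missing data in the self-reported outcomes, so the pooled result over imputed datasets is the one that will be reported. The plan does not say how to obtain it from a test statistic.

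**Working it through.** **1. Can these outcomes be adjusted?** The relevant statements, side by side:

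| Item | Scale in the SAP | Method in the SAP |
|---|---|---|
| Readmission (section 8) | yes/no | log-binomial, adjusted for three factors |
| Self-harm, harm to others, victim of crime (sections 2 and 11) | yes/no, self-reported | as for the primary outcome |
| CAGE alcohol, CAGE drugs (section 5) | yes/no | chi-squared, adjustment said not to be possible |
| Each type of leverage (section 5) | frequency experiencing it | chi-squared, adjustment said not to be possible |
| Adherence, two items (section 2) | how often | chi-squared, adjustment said not to be possible |

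Rows two to four are the same kind of data from the same patients, handled in two ways. As a feasibility check, a robust Poisson model with arm and three binary factors was fitted to simulated trials of 330 patients (the randomisation target in section 3), with assumed event rates and factor prevalences. It converged in 300 of 300.

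**2. Cost of ignoring order (adherence only).** The SAP states no power for these tests, so there is no figure of its own to reproduce. As a reference I take an effect that a one-degree-of-freedom ordered test would detect with 80% power at two-sided 5%.

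- Non-centrality: λ = (1.960 + 0.842)² = 7.849.
- With k categories and two arms, the general chi-squared test has k − 1 degrees of freedom.
- If the whole effect lies in the ordered direction, λ is unchanged and power = P(χ²(k − 1, λ) > c), where c is the 5% critical value.

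| Categories k (assumed) | df | c | Power |
|---|---|---|---|
| ordered test | 1 | 3.841 | 80.0% |
| 3 | 2 | 5.991 | 70.9% |
| 4 | 3 | 7.815 | 64.5% |
| 5 | 4 | 9.488 | 59.5% |

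The loss is about 9, 16 and 20 percentage points. A simulation agrees for five categories. With 165 patients per arm and assumed proportions of 10, 15, 20, 25 and 30% in one arm, chi-squared had 60% power against 81% for a rank test at a common odds ratio of 1.75, and 33% against 54% at 1.5. For a two-category item both tests have one degree of freedom and this loss is zero.

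**3. Pooling.** Ordinary pooling by Rubin's rules combines an estimate and its standard error from each dataset. A chi-squared statistic is neither. Special rules for combining such statistics exist, but the SAP names none.

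**The case against.** The strongest reply is that the sentence in section 10 describes the chosen test: a plain chi-squared test takes no covariates, so no adjustment is possible within it. On that reading the statement is true, and a reader who infers that the SAP denies any possibility of adjusting categorical outcomes goes further than the text requires. What stands is a criticism of the choice of test, which departs from sections 1.3, 8 and 11 without a reason.

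Other points in the plan's favour:

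- Section 5 says that the stratification variables "will be adjusted for in the main analyses". Tertiary outcomes need not be main analyses, so a breach of that rule is arguable at most. Section 1.3 is the firmer comparison.
- Section 10 adds a mixed-effects analysis containing the stratification factors for endpoints measured repeatedly, and does not restrict it to continuous outcomes. The strata are therefore not wholly ignored. It is, however, a sensitivity analysis, and no categorical form is stated.
- A reader might infer that imputation and chi-squared tests are incompatible. They are not, given special pooling rules, and the document does not show what the named command supports. The plan leaves the rule unspecified.
- A reader might also expect inflated type I error. In a simulation with an assumed 35% missing and 20 imputations, averaging the statistics gave 15% and using a single imputed dataset gave 17%, against 4.6% for a pooled log odds ratio. The SAP proposes neither naive method, so these figures show why a rule is needed, not what the plan would do.
- The ordering argument does not extend to CAGE or leverage, and cannot be judged for types of pressure.

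**Conclusion.** The point holds as one of method choice and incomplete specification. The main analysis of the categorical tertiary outcomes is unadjusted and yields no planned estimate or interval, although adjusted models for binary data are already in the SAP. Pooling of the test over imputed datasets has no stated rule.

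Only the loss from ignoring order has been sized: about 71%, 65% or 60% power in place of 80%. That rests on three to five response categories and a pure ordered shift, and it applies to the two adherence items alone. The power lost by leaving out the stratification factors has not been quantified, and no claim about its size is made. The change should be made, but it touches tertiary outcomes only; the primary and secondary analyses are unaffected.

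**What to change.** In section 10 (Tertiary analysis), delete the clause saying that adjustment is not possible and specify:

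- **Binary items** (CAGE alcohol, CAGE drugs, each type of leverage): log-binomial regression, with robust Poisson as fallback, reporting relative risks.
- **The two adherence items:** proportional-odds logistic regression with a check of the proportional-odds assumption, reporting a common odds ratio. State the response categories.
- **Types of pressure:** state the response format and use the matching model.
- **All of these:** adjust for the three stratification factors, fit in each imputed dataset, pool by Rubin's rules and give 95% confidence intervals. Adding the baseline value is optional.
- **Sensitivity analysis:** keep the unadjusted chi-squared test, in line with section 1.3, and name the rule for combining it if it is run on imputed data.

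The cost is a few lines of SAP text, a little more modelling and the assumption check. Rare categories may cause non-convergence, so the fallback should be fixed in advance. No new data are needed.
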